### Date of Last Study Treatment Administration

Date of last study treatment administration is defined as:

- “Date of last application of study drug” as recorded in the ‘Study Termination’ eCRF page.).

### Study Day

The study day of events/assessments is calculated as:

- Study Day = (Date of assessment/event - Date of Baseline Visit).

### Baseline

The baseline value for QOL data is defined as measurements collected on Day 0.

Baseline for data collected through connected activity tracker is derived as an average per day:

- Sum of the variable of interest/baseline period.

Where the baseline period is the number of non-missing days between day -6 to day 0 – Prior to product usage.

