## Footnotes:

a Actigraph tracker is dispensed at screening visit post consent of patient during enrolment for the study (D -7 – Visit 1). and Voltaren is dispensed immediately post eligibility of the subject at the end of Baseline period (Day 0 – Visit 2).

b The questionnaires such as: Pain Visual Analogue Scale (VAS) / Numeric Rating Scale (NRS), will initially be performed on site during enrolment period (Visit 1) and prior to dispensing of Voltaren (Visit 2), to complete the baseline assessment. Subjects are then required to perform the assessment of NRS, Western Ontario and McMaster University Osteoarthritis index (WOMAC), Karolinska Sleepiness Scale and the EQ-5D-5L Health questionnaire at site prior to dispensing of Voltaren (Day 0 – Visit 2) and then at home during the study period and report the score within the eDiary.

c Adverse Events (AEs) and therefore all Serious Adverse Events (SAEs) will be collected immediately after a subject provides consent to participate in the study by the completion of the Informed Consent Form (ICF).

\* Baseline period will be flexible and last a minimum of 3 days and maximum 7 days to collect sufficient baseline information from study subjects. When pain levels reach  $\geq 40$  mm  $\leq 70$ mm in the VAS/NRS scale, the day before starting the use of Voltaren, study subjects will be prompted to answer relevant questionnaires to assess baseline levels. Site staff to monitor subjects eDiary and dispense Voltaren when patients have ended baseline period. Subjects can also notify site staff when their baseline period has ended to commence the study.

\*\* Study period will last a maximum of 28 days. Study subjects are allowed to stop using Voltaren if they feel that their pain has successfully resolved and do not need to use the product anymore.

\*\*\*Urine test only needed for women of childbearing potential and postmenopausal women who are not surgically sterile. Urine samples are collected to detect the presence of human chorionic gonadotropin (hCG), a hormone produced during pregnancy.

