### 5.1.1 Limitations of the study

Given the natural course of OA and pain, data collected during this study may be confounded by the natural course of the disease. Within 24 hours of pain onset, subjects generally report an increase in the severity and number of symptoms they experience.

Given the natural course of the disease, ensuring subjects have access to treatment when OA symptoms are present will allow for subsequent quality of life (QoL) data to be captured, reducing the influence of confounding variables.

Subjects may likely be using other over-the-counter antipyretics/analgesics for severe pain, which may influence their overall Actigraph and QoL data and confound the effect of Voltaren. During this study, subjects will be prompted to report medications they take for symptom relief, along with any changes in medication over the course of their study participation, to better understand the results.

Actigraph is a clinically approved, research-grade, and validated device. It boasts commendable accuracy and applicability in its device and algorithm, ensuring reliable data quality. While some limitations of its usage in a real-world environment may exist, the device's robust design minimises the likelihood of false data, affirming its overall dependability. However, subjects may not be comfortable wearing a wearable device continuously as well as subject non-wear compliance and user related errors may have an impact on the data collected.

At the start of the study, site staff will be given training by Actigraph or relevant trained personnel or through online videos on how to use the device (see tutorial link in appendix), with training on how to use and wear the device appropriately. After receiving training, site staff can then appropriately train subjects, particularly during the dispensing of the product.

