## **9.2 Study Period**

### **9.2.1 Baseline Period**

The number of days each subject will actively engage with the study will be up to 28 days including baseline ([See Appendix](#)).

Study subjects who fulfil criteria and deemed suitable by the investigator for participation will be provided with the Actigraph wearable device which will measure aspects of functional mobility during the baseline period. The baseline period will last between 3 (minimum) and 7 days (maximum), to collect enough information on both subjective and objective aspects of mobility and sleep quality. End of baseline period will be considered day 0.

The baseline period will be variable and will depend on study subjects reaching  $\geq 40$  mm  $\leq 70$  mm of self-reported pain on the pain intensity visual analogue scale (VAS). Once the subject reaches any value at this level on the VAS scale, even for a single observation, the baseline period will be terminated, and study phase can commence.

At the end of the baseline period, the site staff will dispense the study product to the subject to take home and use throughout the study period as per label instructions. Before they start using the product, study subjects will complete the questionnaires to collect information on their baseline levels of quality of life and subjective perceptions of mobility and exercise capacity.

All medications taken during the 60 days prior to the screening visit and throughout the trial (other than study medication) will be recorded on the eCRF.

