### 13.3.2 Secondary Analysis

For the secondary objective, functional mobility as measured through wearables and PRO, pain intensity assessed through NRS (daily assessment), activity-related pain and stiffness as measured in the WOMAC subscales for composite pain and composite stiffness will be analysed using the same MMRM as in the primary objective where the last observed daily value up to Day 0 will be used as the baseline value.

Correlations of quality of life will also be provided as it pertains to the following:

- Sleep/alertness: Karolinska Sleepiness Scale assessed 1x/day.

Property of Haleon - Confidential

May not be used, divulged, published or otherwise disclosed without the consent of  
 Haleon

Clinical Protocol Template, TMF-187821, v11.0. Parent SOP: **CCI**

- Health-related quality of life: EQ-5D-5L.
- Change in the number of study subjects reporting that they feel more in control of their arthritis pain before and after Voltaren use.

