**Change from baseline in self-reported pain intensity, assessed through Numeric Rating Scale (NRS) (daily assessment).**

Self-reported pain intensity is recorded on the 'Numeric Rating Scale' eDiary page at each scheduled timepoint.

Baseline is the value collected on Day 0, as described in section 7.1.

Change from baseline is calculated as:

- NRS score at Scheduled Timepoint – NRS baseline score (Day 0)

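### The NRS baseline is one Day 0 reading taken on a day selected for pain in the 40-70 mm band, so regression to usual pain enters the NRS change, with size and direction unknown

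*SAP*

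**What the plan says.** SAP 7.1 (Baseline) sets the questionnaire baseline: "The baseline value for QOL data is defined as measurements collected on Day 0". SAP 7.4.7.2 repeats it for the NRS: "Baseline is the value collected on Day 0, as described in section 7.1". Protocol 13.3.2 words it a little differently, in that "the last observed daily value up to Day 0 will be used as the baseline value", but that is also a single reading.

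What fixes Day 0 is in Protocol 9.2.1: "End of baseline period will be considered day 0". The same section says that "The baseline period will be variable and will depend on study subjects reaching" 40-70 mm on the VAS, and: "Once the subject reaches any value at this level on the VAS scale, even for a single observation, the baseline period will be terminated". The run-in lasts 3 to 7 days. The footnote to the Schedule of Activities ties the baseline questionnaires to the same event: once pain is in the band, "the day before starting the use of Voltaren, study subjects will be prompted to answer relevant questionnaires to assess baseline levels".

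Tracker endpoints are treated differently. SAP 7.1 averages them over the non-missing days from Day -6 to Day 0.

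The study is single-arm. SAP 8.2.1 tests whether baseline and post-baseline differ, and SAP 8.2.3 applies the primary MMRM to the NRS change on Days 7, 14 and 21.

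**The concern.** Pain fluctuates from day to day. If follow-up starts on a day chosen because pain met a rule, pain on that day is on average displaced from the subject's usual level, and later readings drift back without any treatment. In a single-arm study the estimate is simply later minus baseline, so the drift cannot be separated from a drug effect. Baseline as a fixed effect does not remove it from a mean change in one arm.

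Protocol 5.1.1 concedes that the natural course may confound the data. It then argues that access to treatment when symptoms are present allows "data to be captured, reducing the influence of confounding variables". For the pain endpoint, starting on a symptom-selected day adds regression to the mean. Neither document plans an analysis with another baseline.

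At stake is the secondary objective on pain intensity, which is worded as an effect of Voltaren Gel.

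**Working it through.** **Yardstick.** The plan gives no figure for pain variability, but it is sized for a standardised effect of 0.25 (Protocol 13.1). That sizing reproduces: ((1.960 + 0.842)/0.25)² = 125.6; divided by 0.864, the minimum relative efficiency of the Wilcoxon signed-rank test, this is 145.4, so 146 against the stated 147. For dropout, 147/0.75 = 196 against the stated 195. The sample size is not in question; 0.25 serves only as a scale.

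**Mechanism for one subject.** Let Day 0 pain be u + e, with u the usual level and e a daily fluctuation with SD s. If Day 0 must lie in 40-70 mm and later days are independent, the expected NRS change with no drug effect is −E(e | 40 ≤ u + e ≤ 70)/10. With a = (40 − u)/s and b = (70 − u)/s, E(e) = s[φ(a) − φ(b)]/[Φ(b) − Φ(a)]. Assume s = 10 mm:

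- u = 35: 10 × (0.3521 − 0.0009)/(0.9998 − 0.6915) = 11.4 mm, a change of −1.14 points.
- u = 45: 10 × (0.3521 − 0.0175)/(0.9938 − 0.3085) = 4.9 mm, a change of −0.49 points.
- u = 55, mid-band: a = −1.5 and b = 1.5, so zero.
- u = 65 and u = 75: by symmetry, +0.49 and +1.14 points.

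**Population simulation, no drug effect.** Subjects differ in u, and screening VAS must also be 40-70 mm (inclusion criterion 7). Day 0 is the first in-band day from run-in day 3 to 7; subjects with none are left out, an assumption. NRS is that day's pain/10 plus 0.5-point noise. The outcome is the mean of Days 7, 14 and 21 minus Day 0.

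Set A: between-subject SD 12 mm, day-to-day SD 10-15 mm, day-to-day correlation 0-0.5. Set B: between-subject SD 10-15 mm, day-to-day SD 10-20 mm, independent days. The last two columns are for set B, with a two-sided 5% t test at n = 147.

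| Mean usual pain | NRS change, A | NRS change, B | Standardised | False significance |
|---|---|---|---|---|
| 35 mm | −0.48 to −0.90 | −0.40 to −1.20 | −0.33 to −0.71 | 98-100% |
| 45 mm | −0.24 to −0.46 | −0.20 to −0.62 | −0.16 to −0.36 | 50-99% |
| 55 mm | 0 | about 0 | about 0 | 5% |
| 65 mm | +0.24 to +0.46 | +0.20 to +0.59 | mirror of 45 mm | mirror of 45 mm |
| 75 mm | +0.48 to +0.90 | +0.40 to +1.14 | mirror of 35 mm | mirror of 35 mm |

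**Alternative baselines.**

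- Mean of run-in readings after screening, including Day 0: the artefact falls by about 53-89% (A). In B, −0.06 to −0.16 remains at 35 mm and −0.02 to −0.08 at 45 mm.
- The same mean without Day 0: overshoots, leaving +0.04 to +0.19 at 35-45 mm (B), because the run-in days from day 3 that did not end the run-in are known to be out of band.
- The literal Day −6 to Day 0 window used for the tracker: a cut of only about 44-71% (A). Study day counts back from the baseline visit, so with a 3-day run-in screening falls on Day −3 and its band-selected reading enters the mean.
- Mean of the Visit 1 and Visit 2 NRS: no gain. In A, −0.54 stays −0.54 (35 mm, SD 10, correlation 0), −0.46 stays −0.46 (45 mm, SD 15, correlation 0), and −0.84 becomes −0.86 (35 mm, SD 15, correlation 0.5).

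**The case against.** Four objections deserve an answer.

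*Direction.* A reader might infer that the design builds in a benefit for Voltaren, because subjects wait until pain rises to 40 mm. The documents do not establish this. The band has an upper limit, a flare above 70 mm does not qualify, and nothing states the subjects' usual pain. The mild disease and the wording about reaching the band make a bias in favour of the gel plausible, no more. This objection stands, so the direction must be called unknown.

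*Other endpoints.* A reader might extend the point to every questionnaire. Only the NRS was calculated. WOMAC items ask about the last 48 hours and should be affected less, though WOMAC is still tested from Day 0. KSS measures sleepiness rather than knee pain, and KSS and EQ-5D-5L are summarised without a test (SAP 8.2.3). The primary MVPA endpoint already has an averaged baseline and is outside this point.

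*Data.* Averaging needs run-in NRS values. The schedule marks NRS in the D-7 to D0 column, SAP Table 3 lists Days −6 to −1, and site staff monitor the eDiary during run-in. Yet schedule footnote b describes pre-treatment NRS only at the two site visits, and Protocol 10.2 starts daily completion at receipt of product. The readings are likely but not assured.

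*Already acknowledged.* Protocol 5.1.1 names natural-course confounding, and attribution is limited in any single-arm study. True, but an acknowledgement does not reduce the bias, and the SAP already averages the baseline for the tracker.

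**Conclusion.** The concern holds for the NRS. The baseline is a single reading, on a day fixed by a rule about pain, in a study with no control, and the change is tested. With no drug effect this can produce a standardised change around or above the 0.25 used for sizing when mean usual pain lies about 10 mm or more from mid-band, in either direction; near 55 mm it produces almost nothing.

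These sizes rest on assumed means, SDs and day-to-day correlation, and on the Day 0 NRS being taken on the same day as the in-band reading, as the documents describe. If Visit 2 followed the triggering reading by a day or more, the part due to that reading would be smaller. Selection at screening remains under any new definition of baseline. The documents do not support the stronger claims that the NRS result is biased towards the gel or that all questionnaire results are compromised.

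**What to change.** - In SAP 7.1 and 7.4.7.2, keep the Day 0 NRS analysis. Prespecify a second one whose baseline is the mean of all non-missing NRS readings after the screening visit, up to and including Day 0 and before first gel use, for subjects who have such readings. Tabulate how many do.
- Do not fall back on the Visit 1/Visit 2 average: Visit 1 is selected on the same band, and the bias is unchanged.
- Report NRS and WOMAC results as change from baseline, not as an effect of the gel alone, and say that the direction of the selection bias is unknown.
- Do not rely on the Protocol 5.1.1 statement about reduced confounding when interpreting these results. This needs no protocol amendment.
- Leave KSS and EQ-5D-5L as they are.

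The cost is one derivation, one table and a further SAP version. SAP 2.0 already follows the data review meeting in an open-label study, so the addition should be dated and labelled as such. The NRS change may come out smaller or larger than with Day 0.

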### 3.3 Study Schedule

**Table 1: Schedule of Events**

Procedure/Assessment	Screening and Enrolment	Baseline *	Study Treatment Phase **						
	Day -7 (Visit 1)	D-7 to D0 (Visit 2)	D1	D1 to D6	D7	D8 to D13	D14	D15 to D20	D21 (Visit 3)
Informed Consent	X								
Inclusion/Exclusion Criteria	X								
Medical History	X								
Demographics	X								
Current/Prior concomitant medication review	X	X	X	X	X	X	X	X	X
Subject Eligibility	X								
Study Product use			X	X	X	X	X	X	X
Urine Pregnancy Test***	X								X

Procedure/Assessment	Screening and Enrolment	Baseline *	Study Treatment Phase **						
	Day -7 (Visit 1)	D-7 to D0 (Visit 2)	D1	D1 to D6	D7	D8 to D13	D14	D15 to D20	D21 (Visit 3)
Dispensing of (Actigraph) a	X								
Dispensing of Product (Voltaren) a		X							
Pain									
Numeric Rating Scale b	X	X	X	X	X	X	X	X	X
Visual Analogue Scale b	X	X							
Western Ontario and McMaster University Osteoarthritis index (WOMAC) Pain Subscale b		X	X		X		X		X
Mobility									
Tracker-derived mobility assessment c		X	X	X	X	X	X	X	X
Western Ontario and McMaster University Osteoarthritis index (WOMAC) Stiffness Subscale b		X	X		X		X		X
Western Ontario and McMaster University Osteoarthritis index (WOMAC) Function Subscale b		X	X		X		X		X
Sleep									
Tracker-derived sleep assessment		X	X	X	X	X	X	X	X
Karolinska Sleepiness Scale b		X	X	X	X	X	X	X	X
Quality of Life									
EQ-5D-5L Quality of Life Questionnaire		X	X		X		X		X
Safety									
Adverse Events (AEs) Review c	X	X	X	X	X	X	X	X	X
Study Conclusion									
Returning Actigraph device and the allocated product									X
End of Study Questionnaires									X

a. Actigraph tracker is dispensed at screening visit post consent of patient during enrolment for the study (D -7 – Visit 1) and Voltaren is dispensed immediately post eligibility of the subject at the end of Baseline period (Day 0 – Visit 2).

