### Actigraph Device Compliance

The required Actigraph daily minimum wear time is 20 hours. Daily wear minutes is collected via the Actigraph device and converted to hours as:

- Daily wear time (hours) = Daily wear minutes ÷ 60.

Actigraph device compliance is calculated as:

- Actigraph device compliance (%) = (Number of days the daily wear time (hours) is greater than or equal to 20 hours ÷ Total number of days on study) \* 100

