## **7.4.7 Efficacy Variables**

### **7.4.7.1 Primary Efficacy Variable**

For primary analysis, average minutes of MVPA on Day 7 will be calculated over all non-missing days between study day 1 (product usage) through 7, inclusive and it is collected via the Actigraph device. Average minutes of MVPA on Day 14 will be calculated over all non-missing days between study day 8 through 14, inclusive. Average minutes of MVPA on Day 21 will be calculated over all non-missing days between study day 15 through 20, inclusive. Any days beyond day 20 will be excluded from all summaries and analyses and will only be present in listed data.

Average baseline MVPA is computed as:

- Average baseline MVPA = total minutes of MVPA over the baseline period / number of days with non-missing data over the baseline period.
  - Baseline period is defined in section 7.1.

Average MVPA for each 7-day period is calculated as:

- Average MVPA for 7-day period = total minutes of MVPA over the period / number of days with non missing data over the period.
  - If every day within the 7 – day period has non missing data, then the Average MVPA for 7- day period will be computed as: total minutes of MVPA over the period / 7.

Change from baseline is calculated as:

- Average MVPA for 7-day period - Average baseline MVPA.

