### **7.4.7.2 Secondary Efficacy Variables**

#### **Change from baseline on Days 7, 14, and 21 in Daily Average number of steps taken**

Average baseline number of steps taken is calculated as:

- Average baseline number of steps taken = total number of steps taken over the baseline period / number of days with non missing data over the baseline period.
  - Baseline period is defined in section 7.1.

Daily average number of steps taken for each 7-day period is calculated as:

- Daily average number of steps taken for 7-day period = total number of steps over the period / number of days with non missing data over the period.

Change from baseline is calculated as:

- Daily average number of steps taken for 7-day period - Average baseline number of steps taken.

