### 8.2 Specific Methods for Efficacy Analyses

For the primary and secondary endpoints where the data is collected through the activity tracker, only subjects who meet the minimum wear threshold will be included in the analysis. This is defined as a minimum of 3 valid days during the baseline period and a minimum of 3 valid days within each post-baseline 7-day period, where a valid day is defined as a minimum wear of 20 hours per day.

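### For baselines of 3 to 6 days, the part-recorded device-dispensing day is averaged as a full day, which lowers baseline MVPA and steps and creates a false gain

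*SAP*

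**What the plan says.** SAP 7.1 (Baseline) averages each tracker variable per day over a fixed window: "Where the baseline period is the number of non-missing days between day -6 to day 0". The window is anchored by the rule "Study Day = (Date of assessment/event - Date of Baseline Visit", so the baseline visit is Day 0. SAP 7.1 also says that external data, which include the tracker, follow this calculated day and not the visit label.

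Footnote a to the SAP schedule states: "Actigraph tracker is dispensed at screening visit post consent of patient during enrolment for the study". Protocol 9.2.1 lets the baseline run from 3 to 7 days, and once a VAS reading is in range, "even for a single observation, the baseline period will be terminated".

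SAP 7.4.7.1 computes baseline MVPA as "total minutes of MVPA over the baseline period / number of days with non-missing data over the baseline period". Section 7.4.7.2 does the same for steps: "total number of steps taken over the baseline period / number of days with non missing data over the baseline period". Neither section defines a non-missing day.

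Wear time appears in two other places. SAP 7.4.6 says "The required Actigraph daily minimum wear time is 20 hours". SAP 8.2 says "only subjects who meet the minimum wear threshold will be included in the analysis", meaning at least 3 days of 20 hours or more in the baseline and in each later 7-day period. The last analysis week stops at Day 20; the SAP Document History gives the reason that Day 21 is partial.

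**The concern.** The device goes on during a site visit, so the tracker misses the earlier part of that calendar day. MVPA minutes and steps are daily totals. A part-recorded day therefore adds a truncated amount to the numerator and a full unit to the denominator. If that day lies in the baseline window, the baseline is too low on average and every later change from baseline is too high by the same amount.

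Ordinary low-wear days can fall in any period. The dispensing day can fall only in the baseline, so its error runs one way, in favour of the product. There is no control arm to cancel it, and repeated-measures modelling does not repair a baseline that was computed too low. The SAP recognised the partial-day problem at the end of follow-up but has no matching rule at the start for shortened baselines.

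**Working it through.** **The plan's own figures.** The documents give no figure for this bias. Their one calculation is the sample size: effect 0.25, two-sided 5%, 80% power, Wilcoxon signed rank. A paired calculation with the minimum Wilcoxon efficiency (0.864) gives 148 completers, against 147 stated; 147/0.75 = 196, against 195 enrolled. Both reproduce closely enough. Only n = 147 is used below.

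**Step 1: where the dispensing day falls.** Let L be the days from screening to the baseline visit, so dispensing is on Day -L.
- L = 7: Day -7, outside the window. The window holds 7 days, and the bias is 0.
- L = 3 to 6: inside the window. It holds L + 1 days, one of them part-recorded.

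**Step 2: size per subject.** Let m be the true daily mean and f the share of the dispensing day's activity captured (assumed). On average:

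computed baseline = m(L + f)/(L + 1), so the understatement is (1 - f)/(L + 1).

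| L (days) | f = 0.25 | f = 0.5 | f = 0.75 |
|---|---|---|---|
| 3 | 18.8% | 12.5% | 6.3% |
| 4 | 15.0% | 10.0% | 5.0% |
| 5 | 12.5% | 8.3% | 4.2% |
| 6 | 10.7% | 7.1% | 3.6% |
| 7 | 0 | 0 | 0 |

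If activity is even from 07:00 to 23:00 (16 h), f = 0.75 means dispensing at 11:00, 0.5 at 15:00 and 0.25 at 19:00. The last is an outer limit.

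**Step 3: average over all subjects.** At f = 0.5 the mean over L = 3 to 6 is (12.5 + 10.0 + 8.33 + 7.14)/4 = 9.49%. The gain in minutes assumes a mean MVPA of 40 min/day.

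| Share of short baselines | Understatement | False gain (min/day) |
|---|---|---|
| A quarter | 0.25 × 9.49 = 2.4% | 1.0 |
| Half | 0.50 × 9.49 = 4.7% | 1.9 |
| Lengths even over 3 to 7 | 0.80 × 9.49 = 7.6% | 3.0 |
| All L = 3 | 12.5% | 5.0 |

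**Step 4: effect on a test.** Take an unadjusted one-sample t test of one week's change, with n = 147 and no true effect. If the SD of change equals mean MVPA, the false standardized effect equals the understatement. For all L = 3 it is 0.125, half the design effect of 0.25. The noncentrality is 0.125 × √147 = 1.52, and the test rejects about 33% of the time.

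A day-level simulation (10,000 replicates; assumed mean 40, between-subject variance 720, day variance 1260) gave these rejection rates as the SD of change goes from 1.0 down to 0.48 of the mean:

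| Share of short baselines | f = 0.5 | f = 0.75 |
|---|---|---|
| A quarter | 6–9% | 6% |
| Half | 9–21% | 6–9% |
| Even 3 to 7 | 15–45% | 7–15% |
| All L = 3 | 34–81% | 12–29% |

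If all baselines last 7 days, the rate is 4.9–5.5%. With the dispensing day excluded (a quarter, even, all L = 3) it is 4.7–5.3%.

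**Step 5: does the 8.2 wear rule remove it?** No. A subject with L = 3 has three full days in the window (Days -2 to 0) and qualifies if all three are valid. At an assumed 0.9 chance per day, 0.9³ = 73% stay in, and their dispensing day is still averaged. With the rule applied at f = 0.5, rejection is 6–8%, 14–40% and 26–67% for a quarter, even and all L = 3.

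**The case against.** **Non-missing is undefined.** If programmers set days under 20 hours to missing, the bias vanishes. The data management plan, dataset specifications and table shells are separate documents and might say so. This is fair as far as it goes. But the SAP ties the 20-hour rule to subjects and never uses a valid day in the averaging formulas. Removing Day 21 by an explicit rule also suggests that partial days do not drop out by themselves.

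**The Day -6 start already drops the dispensing day.** It does so on the scheduled timetable, where screening is Day -7. This stands and limits the problem to shortened baselines.

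**Exposure and variances are unknown.** This stands. If a quarter of baselines are short and f = 0.5, the inflation is modest. The highest rates need an SD of change of 0.48 of the mean. Day noise alone gives √(1260 × 2/7)/40 = 0.474, so that case leaves almost no real week-to-week variation and is a boundary.

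**The simulated test is not the planned one.** Also true. The planned first step tests the intercept of a model with baseline as a covariate, and these are not its error rates. In the non-normal branch, a Friedman test on the three weekly changes would cancel a constant baseline error within each subject; the SAP does not settle which values are ranked. The displaced mean change remains whichever test is used.

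**The share f is assumed,** and a visit day may differ from an ordinary day. This affects the size. The expected direction holds as long as the tracker misses part of the day's activity.

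**Conclusion.** The concern holds on the SAP as written. For any subject with a baseline of 3 to 6 days, the derivation includes a part-recorded day and understates baseline MVPA and steps on average. That existence and expected direction follow from the SAP's definitions and on-site dispensing.

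The size rests on assumptions. Per affected subject it is 7.1–12.5% at f = 0.5, and 3.6–18.8% over f from 0.25 to 0.75. Across the study at f = 0.5 it runs from 2.4% if a quarter of baselines are short to 12.5% if all last 3 days. The false-positive rates are illustrations for a simple test under assumed variances.

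Short baselines are plausible because entry already requires pain in the range that ends the baseline, subject to the 3-day minimum. The sponsor can count them from the Visit 1 and Visit 2 dates. A one-sided error favouring the product in the primary endpoint of a single-arm study must be fixed. No bias is claimed for the other tracker endpoints.

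**What to change.** In SAP 7.1, in 7.4.7.1 and in the step-count derivation in 7.4.7.2:

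1. Exclude the device-dispensing date from the tracker baseline, whatever its study day. This alone removes the bias.
2. Define a non-missing day as a valid day under 8.2 (at least 20 hours of wear) and average both baseline and weekly values over valid days only. This closes the ambiguity and treats all periods alike. Use the same day filter for the other tracker endpoints for consistency.
3. Tabulate baseline length, so that readers can see how many subjects were affected.

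The cost is SAP wording and a filter on wear minutes already collected under 7.4.6. Some averages will rest on fewer days, and item 2 may drop days with full waking wear but under 20 hours in total. No subject is lost: 20 hours on the dispensing date would need the device on by 04:00, so a day of on-site dispensing could not have been one of the three valid baseline days that 8.2 requires. The planned sample size is unchanged. The fix does not address how the intercept test in the first primary model is interpreted, which is a separate matter.
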